3 OVERALL STUDY DESIGN

This is a prospective, open-label, two-arm, 2:1 randomized phase III study. The efficacy of plitidepsin in combination with dexamethasone (Arm A) vs. dexamethasone alone

(Arm B) will be studied by means of PFS calculated using the IMWG uniform response criteria (Appendix 5), and the evaluation of secondary efficacy endpoints.

Patients in the control arm (dexamethasone alone, Arm B) who have documented disease progression according to the Investigator's criteria after a minimum of eight weeks from randomization should be offered crossover to combination arm (plitidepsin + dexamethasone, Arm A) upon Sponsor agreement.

An Independent Review Committee (IRC), consisting of medical specialists directly involved in the care of MM patients, but not being investigators or subinvestigators in this trial, will review all efficacy data and will assign the date of progression/censoring and objective response according to their independent evaluation. This IRC will be blinded to treatment arm allocation and identity of the cases reviewed (Section 5.6).

An Independent Data Monitoring Committee (IDMC), including specialists in MM and in medical statistics, will review the results of the analysis performed by an independent statistician. Then, the IDMC will advise the Sponsor about the study conduct.

Operational details for the above mentioned IRC and IDMC will be detailed in the corresponding charters.

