4.1 Analysis sets definitions

“All Randomized Patients” analysis set is defined as all patients who are randomized to either treatment arm, independent of whether they received the study drug.

“All Treated Patients” analysis set is defined as all randomized patients who receive at least part of one dose or infusion of the investigational agents.

“All Evaluable Patients” analysis set is defined as all randomized patients who have completed at least one full cycle of treatment or have received two incomplete cycles followed by at least one response assessment not less than eight weeks (\pm one week) after treatment onset. Patients withdrawn from the study due to early disease progression or treatment-related toxicity will be considered as “early progression” or “treatment failure”, respectively, even though they have not received a full cycle. Patients withdrawn due to significant clinical deterioration of unknown reason, hypersensitivity reactions, or refusal to continue on study for any reason or unrelated AEs without any disease assessments after the start of study treatment or those patients with a protocol deviation resulting in an impossibility of drawing conclusions about the efficacy of the study therapy will be considered not evaluable for efficacy and their response will be categorized as “non evaluable”.

“All Responder Patients” analysis set is defined as all evaluable patients who have minor response or better as overall best response.

“All Crossover Patients” analysis set is defined as all patients randomized to Arm B who have documented disease progression after their eighth week from randomization and cross over to Arm A.

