DR for patients who have PR or better as best overall response based on the IMWG criteria will be calculated as a supportive analysis.

Time to response:

Time to response will be analyzed according to the Kaplan-Meier method and compared between treatment groups using the log-rank test.

Time to response for patients who have PR or better as best overall response based on the IMWG criteria will be also calculated as a supportive analysis.

Analysis of crossover:

Descriptive frequency tables with the number of patients who switch from Arm B to Arm A after disease progression will be calculated.

Exploratory intrapatient comparison of response and PFS (before and after crossover) will be performed for patients who switch from Arm B to Arm A after disease progression.

The patients within the “All Crossover Patients” dataset will be listed with the cycle when the crossover occurs, and the response and PFS before and after crossover.

A comparison of the baseline characteristics in patients with Crossover *vs.* No crossover will be done to rule out that patients with crossover can have a better prognosis than patients without crossover. For two-stage method a logistic stepwise regression and the comparison of PFS between patients with crossover versus patients with no crossover is performed to check the assumption of no ‘unmeasured confounders’. Post-progression survival data is adjusted by a Weibull parametric accelerated failure time model.

A listing of patients with crossover will be provided in order to confirm if PD was seen before crossover and if this PD was confirmed.

Statistics of the time (in months) from study initiation to crossover will also be included.

Analysis of prognostic factors, subgroup analysis and multivariate analyses:

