11.3.2 Supportive PFS analyses

In the ‘time-to-event variables’, the unstratified and stratified log-rank test will be used to evaluate the differences between treatment arms and the median values of time-dependent parameters. Their fixed-time estimations will be analyzed according to the Kaplan-Meier method. Median follow-up assessments will be calculated using the Kaplan-Meier method reversing the censoring values (5). Whenever it is not specified, the unstratified test is used.

Table 11.3.2.1 PFS (Investigator Assessment and “All Randomized Patients” population)

	Arm A	Arm B	Parameter	p-value
N				
Events				
Censored				
Median PFS			Log-Rank: HR (95% CI) :	LR: HR:
PFS at 6 months			Diff:	

Kaplan-Meier plot will be also shown (Figure 11.3.2.1)

Table 11.3.2.2 PFS (Independent Review assessment and “All Randomized Patients” population). Stratified.

	Arm A	Arm B
Stratum 1		
N		
Events		
Censored		
Median PFS		
PFS at 6 months		
Stratum 2		
N		
....		
....		
Log-Rank* / p-value** / HR (95% CI) :		

(*)Stratified log-rank test statistic. (**) p-value from stratified log-rank test

Table 11.3.2.3 PFS (Investigator Assessment and “All Randomized Patients” population). Stratified comparison.

	Arm A	Arm B
Stratum 1		
N		
Events		
Censored		
Median PFS		
PFS at 6 months		
Stratum 2		
N		
Events		
....		
....		
Log-Rank* / p-value** / HR (95% CI) :		

(*)Stratified log-rank test statistic. (**) p-value from stratified log-rank test

Table 11.3.2.4 PFS – Concordance between Independent Review assessment and Investigator assessment (“All Randomized Patients” population)

	Arm A (N=XX)		Arm B (N=YY)		Total (N=ZZ)	
	N	%	N	%	N	%
Event by investigator						
Agreement on event						
Same date						
Later date						
Earlier date						
Censored by investigator						
Agreement on censoring						
Same date						
Different date						
Agreement on status						
Agreement on status and date						

XX, YY, ZZ = Patients evaluable for both Independent review assessment and investigator assessment

Table 11.3.2.5 PFS – Reason of censoring (“All Randomized Patients” population)

Reason of censoring	Independent review assessment				Investigator assessment			
	Arm A		Arm B		Arm A		Arm B	
	N	%	N	%	N	%	N	%
Lost to follow-up								
Subsequent therapy								
>1 missing assessment								
Still on treatment								
...								

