Kaplan-Meier plot will be also shown (Figure 11.3.4.1.9).

Table 11.3.4.1.10 OS (Subpopulation of patients with event in the primary analysis and without crossover or subsequent therapy)

	Arm A	Arm B	Parameter	p-value
N				
Events				
Censored				
Median OS			Log-Rank: HR (95% CI) :	LR: HR:
OS at 12 months			Diff:	
OS at 24 months			Diff:	

Kaplan-Meier plot will be also shown (Figure 11.3.4.1.10).

Table 11.3.4.1.11 OS (“All Randomized Patients” population and Two-stage method)

	Arm A	Arm B	Parameter	p-value
N				
Events				
Censored				
Median OS			Log-Rank: HR (95% CI) :	LR: HR:
OS at 12 months			Diff:	
OS at 24 months			Diff:	

Kaplan-Meier plot will be also shown (Figure 11.3.4.1.11).

A forest plot (Figure 11.3.4.1.12) with the summary of hazard ratios for OS in the different analysis populations will be shown to check the consistency across the different measurements.

Supportive analyses needed to adjust OS by crossover by the two-stage method

Table 11.3.4.1.13 Logistic regression (Crossover patients vs no crossover patients)

Analysis of Maximum Likelihood Estimates*								
Variable Label	Variable values	DF	Parameter Estimate	Standard Error	Chi-Square	Pr > ChiSq	Odds Ratio	95% Odds Ratio Confidence Limits

* Logistic regression

See list of covariates in section 6.2.3

Table 11.3.4.1.14 PFS (Crossover patients vs no crossover patients)

	Crossover	No crossover	Parameter	p-value
N				
Events				
Censored				
Median PFS			Log-Rank: HR (95% CI) :	LR: HR:

Kaplan-Meier plot will be also shown (Figure 11.3.4.1.14).

Table 11.3.4.1.15 Post progression survival (Weibull adjustment)

Analysis of Maximum Likelihood Parameter Estimates							
Parameter		DF	Estimate	Standard Error	95% Confidence Limits	Chi-Square	Pr > ChiSq
Intercept							
Treatment arm	-						
Treatment arm	Crossover						
Scale							
Weibull Shape							

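### The two-stage OS method's planned check cannot verify no unmeasured confounding, and its PFS comparison largely reflects the 8-week crossover rule unless limited to eligible patients

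*SAP*

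**What the plan says.** SAP 6.2.3, Analysis of crossover, names two tools for the two-stage method. One is a stepwise logistic regression. For the other it says that "the comparison of PFS between patients with crossover versus patients with no crossover is performed to check the assumption of no" unmeasured confounders. The table shell in SAP 11.3.4.1 is "Table 11.3.4.1.14 PFS (Crossover patients vs no crossover patients". It has rows for median PFS, log-rank, hazard ratio and p-values. It names no population, no landmark and no PFS assessor (IRC or Investigator). SAP 11.3.2 sets the default test: "Whenever it is not specified, the unstratified test is used".

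The crossover rule is in Protocol section 3, for control patients who have "documented disease progression according to the Investigator's criteria after a minimum of eight weeks from randomization should be offered crossover". SAP 4.1 defines the crossover set as Arm B patients "who have documented disease progression after their eighth week from randomization and cross over to Arm A".

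The revision history for SAP v6.0 explains the method. Progression serves as a second baseline in the control group, and the estimate is reasonable only if, among other conditions, no unmeasured confounders are present at that point.

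**The concern.** The assumption concerns the moment of progression: no unrecorded factor may drive both the decision to switch and survival afterwards. The two planned tools answer other questions. The logistic regression asks which of the covariates listed in 6.2.3 go with switching, so an unrecorded factor cannot appear in it. The log-rank test asks whether PFS from randomization is the same in later switchers and non-switchers.

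That second question is distorted by the design. A patient must reach about week 8 without progression to be able to switch. Unless the comparison group is restricted, it holds the early progressors and those who die without progression. Switchers therefore have a stretch of guaranteed PFS, and the curves differ even if switching is decided at random.

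The check can mislead in both directions. A significant result may discredit a sound adjustment. A non-significant one may be taken as support that it does not give.

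**Working it through.** The plan states no figure for this check, so there is none to reproduce.

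**Inputs.** Arm B has about 83 patients (SAP 5.2). The planning examples give control median PFS *m* = 10, 12 or 16 weeks (SAP 5.2). Assessment is every 4 weeks (SAP 6.1.2). The share of eligible patients who switch is not given; 30%, 50% and 90% are assumed. Exponential PFS, and a comparison within Arm B, are also assumed.

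**Early events by hand.** P(PFS < *t*) = 1 − 2^(−*t*/*m*). At *t* = 8 weeks this is 43%, 37% and 29% for *m* = 10, 12 and 16. If progression found at the week-8 visit counts as eligible, only events found at week 4 are excluded: 1 − 2^(−4/10) = 24% for *m* = 10.

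For *m* = 10 that is 83 × 0.242 = 20.1 early patients and 62.9 eligible ones. If half switch at random, the non-crossover group is 20.1 + 31.4 = 51.5, of whom 20.1/51.5 = 39% have their event by week 4. In the crossover group the figure is 0%. If 90% switch, the non-crossover share is 20.1/(20.1 + 6.3) = 76%. The contrast grows with the switching share.

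**Simulation, random switching, no confounding.** Percentage of trials with log-rank p < 0.05 (two-sided), 2000 trials per cell, no deaths without progression; *m* = 10/12/16:

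| Eligible patients switching | Week-8 PD eligible | Week-8 PD not eligible |
|---|---|---|
| 30% | 22/17/12 | 52/39/30 |
| 50% | 50/41/27 | 89/80/62 |
| 90% | 99/97/91 | 100/100/100 |

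Taking 10% of events as deaths without progression (assumed), the week-8-eligible rates are about 12-21%, 26-49% and 82-98% in the three rows. Half switching with week-8 PD not eligible gives 84/76/58. Dating 30% of progressions one visit earlier, to mimic IRC and Investigator disagreement, moves the half-switching figures (week-8 PD not eligible) from 89/80/62 to 87/78/62.

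**Comparator limited to progressed patients.** With week-8 PD eligible, rates are 46/36/26 at 50% switching and 99/97/88 at 90%. Early progressors remain in the group, so the distortion remains.

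**Comparator limited to eligible patients.** Rejection is about 5% (5-7% across cells) and the hazard ratio is about 1.0. The excess therefore comes from the 8-week rule.

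**Adding a hidden factor** (half switching, continuous PFS times; rate without the factor 87/81/65):
- Raises the PFS hazard (HR 2), and fitter patients switch more (odds ratio 3): 97/92/84 unrestricted; 9-11% among eligible patients.
- HR 3, odds ratio 5: 99/98/95 unrestricted; 19-22% among eligible patients.
- HR 3, with sicker patients switching more (odds ratio 1/5): falls to 54/42/24 unrestricted, and the hazard ratio still favours crossover.
- Affects switching but not PFS (odds ratio 5): 86/80/63 unrestricted, which is about the rate without it; 5-6% among eligible patients.

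**What an unseen factor could do.** Suppose half of patients carry it and switch with probability 0.9 against 0.4. Carriers are 0.9/1.3 = 69% of switchers and 0.1/0.7 = 14% of non-switchers. If it doubles post-progression survival, the ratio of mean survival is 1.69/1.14 = 1.48 with no true effect of switching. If it triples survival, the ratio is (1 + 2 × 0.692)/(1 + 2 × 0.143) = 1.85. These are illustrations that assume no recorded variable captures any of the factor.

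**The case against.** The strongest reply is that the comparison group is undefined. The table sits among the analyses supporting the two-stage method, which starts at progression, so patients without progression may not belong in it. That is a fair reading, but limiting the group to progressed patients leaves the result nearly unchanged, as shown above. Only restriction to eligible patients removes the artefact, and neither SAP 6.2.3 nor the shell says that.

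A reader might go further and infer that the PFS comparison carries no information about confounding. The working does not support this. A hidden factor acting on both PFS and switching moves the rejection rate clearly, and PFS is itself a measured prognostic variable, so an imbalance in it is worth seeing. The zero-power result needs a factor unrelated to PFS. ECOG, hemoglobin and other recorded values may also capture part of any fitness difference.

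The limited impact also stands. The two-stage analysis is one of five planned for crossover (exclusion, censoring, RPSFT, IPCW, two-stage). All are conditional on OS being materially influenced by crossover, and the revision history calls the two-stage analysis supportive. RPSFT does not rest on this assumption. No decision rule hangs on the check, and the revision history already lists the assumption as a condition.

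**Conclusion.** The point holds. SAP 6.2.3 presents two analyses as a check of an assumption that neither can verify, and the PFS comparison as specified is largely driven by the 8-week rule. The size rests on exponential PFS at the planning medians, 83 control patients, an unknown switching share and an unstated treatment of week-8 progression. With week-8 progression eligible, false signals run from about 12% of trials at 30% switching to 98% at 90%.

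A reader might infer that a significant result is to be expected even without confounding. That is true only when many eligible patients switch or week-8 progression does not qualify; at half switching with week-8 progression eligible the rate is below or about one half. Nor do the documents support reading this as a flaw in the primary PFS analysis, the error control or the unadjusted OS comparison. What is affected is how far the two-stage OS estimate can be trusted. The change is worth making but is not critical.

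**What to change.** 1. In SAP 6.2.3, replace the statement that these analyses check the assumption with one that the assumption cannot be tested from the data.
2. Restrict Table 11.3.4.1.14 to Arm B patients with Investigator PD at or after week 8, applying the same week-8 convention as was used for offering crossover. Name one PFS assessor. Present the table as a description of measured imbalance, without p-values.
3. In the same patients, show standardized differences between switchers and non-switchers in values at progression already listed for IPCW: ECOG, M-protein, hemoglobin, creatinine, LDH, corrected calcium and number of grade 3 or higher adverse events.
4. Beside Table 11.3.4.1.11, add a tipping-point table showing how strong an unmeasured factor would have to be, in its links to switching and to post-progression survival, to move the two-stage OS hazard ratio to 1.

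The cost is SAP wording, one revised shell and two short tables from data already collected. The downside is that the two-stage result will read as less certain.

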2 STUDY DESIGN

This will be a prospective, multicenter, open-label, two-arm, 2:1 randomized phase III study of plitidepsin in combination with dexamethasone vs. dexamethasone alone in patients with relapsed/refractory MM.

The primary study endpoint is progression free survival (PFS).

- Treatment Arm A:
 - Dexamethasone: 40 mg orally on Day 1, 8, 15 and 22 every four weeks (q4wk) at least one hour before plitidepsin infusion.
 - Plitidepsin: 5 mg/m² intravenously (i.v.) diluted to a total volume of 250 ml in 0.9% saline via a central venous catheter (suggested) or diluted to a total volume of 500 ml in 0.9% saline via a peripheral line. Infusion will be performed through a pump device over three hours (fixed rate) on Day 1 and 15 q4wk.

- Treatment Arm B:
 - Dexamethasone: 40 mg orally on Day 1, 8, 15 and 22 q4wk.

Patients in the control arm (dexamethasone alone, Arm B) who have documented disease progression after a minimum of eight weeks from randomization should be offered to cross over to combination arm (plitidepsin + dexamethasone, Arm A) upon Sponsor agreement.

Patients may be treated with additional cycles of plitidepsin and dexamethasone or dexamethasone alone, as long as no unacceptable toxicity and/or disease progression is documented.

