
15 Revision History

From Statistical Analysis Plan v5.0 to v6.0:

This amendment of the Statistical Analysis Plan (SAP) is intended to incorporate an additional overall survival sensitivity analysis in order to better characterize the impact of crossover in arm B. The addition of this new analysis was consulted and agreed with the EMA Product Team Members in a clarification meeting that took place on 12th of June of 2017.

The nature of these analyses is supportive for the secondary analyses of overall survival already described in previous versions of the SAP.

Rational of changes:

In order to improve the characterisation of the actual impact of crossover in those patients who switched from DXM (Arm B) to plitidepsin plus DXM (Arm A), an analysis based on the two-stage method proposed by Latimer *et al.* (7) is performed.

Briefly, the two-stage estimation is a method that provides a good fit to the treatment change mechanics often observed in oncology. Usually, switching is only permitted after disease progression, but this is likely to occur shortly afterwards. In that case, disease progression can be used as a secondary baseline for patients in the control group. Fitting a Weibull model would be expected to produce a reasonable estimate of the effect resulting from switching to the experimental treatment, provided that 1) the model fits the data, 2) “no unmeasured confounders” are present at the secondary baseline, and 3) switching occurs soon after the secondary baseline. The resulting acceleration factor associated with treatment change could then be used to “shrink” survival times in switching patients to derive a counterfactual survival dataset upon which standard survival analysis could be undertaken.

CHANGES:

Included changes are highlighted in *Italic Bold*.

PAGE 16-17: Section 6.2.3 Secondary analyses – Overall survival

Original text:

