After discussion with the agencies personnel who will be involved in the assessment of the centralized procedure for Aplidin, the sensitivity analysis of PFS taking into account the confirmation of PD has been pointed out as a key sensitivity analysis to put in context the results of Admyre. Thus, not only the univariate analysis of PFS with confirmation of PD by IA, IRC but also subgroup analysis, and analysis of other secondary endpoints like DR using this second algorithm for determination of PD will be added to the set of sensitivity analyses.

In line with the discussion on the management of patients with or without confirmation of PD, a measure of the time from randomization to treatment failure that leads to the need of a further treatment regimen (regardless the method of PD detection or the components of the PD) could be the Time to first subsequent therapy or death. This will be included as supportive analysis.

An analysis of the median time window between the first PD and its confirmation in a second assessment has been requested to rule out that confirmation of PD could have been advanced or delayed in any of the treatment groups.

Multivariate analyses of PFS by IRC (adding region as a covariate) have been added to check if there are differences in the main efficacy endpoint between different continents/geographical areas.

Since the clinical benefit in terms of objective response is measured in different studies and along the different response criteria versions with and without taking into account the MR, a sensitivity analysis of response and its duration will be performed taking into account response equal PR or better. In addition, time to response with and without MR will be added.

The SAP includes different secondary analyses of OS taking into account a potential effect of crossover. It has been hypothesized that patients without crossover or subsequent therapies could have a worse prognosis. Analyses will be carried out to investigate the isolated effect of study treatments in survival in the population of patient without subsequent therapy.

Supportive analysis to describe potential effects of the study drugs in QoL has been requested. Since patient reported outcome questionnaires have not been collected in this study, an indirect measure like time to first performance status deterioration have been added.

CHANGES:

Included changes are highlighted in *Italic Bold*.

PAGE 5: ABBREVIATIONS AND GLOSSARY

ADDED

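### The two-stage crossover adjustment of OS names no covariates for its Weibull model, so if crossover patients have the better prognosis the adjusted hazard ratio is biased towards plitidepsin

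*SAP*

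**What the plan says.** - **The model (SAP 6.2.3, Analysis of crossover).** The only sentence on the outcome model is "Post-progression survival data is adjusted by a Weibull parametric accelerated failure time model". No covariates are named.
- **The checks (same paragraph).** The preceding sentence says that "a logistic stepwise regression and the comparison of PFS between patients with crossover versus patients with no crossover is performed to check the assumption", namely that there are no unmeasured confounders. Nothing says that the result of either check is carried into the Weibull model.
- **The output (SAP 11.3.4.1).** The shell is "Table 11.3.4.1.15 Post progression survival (Weibull adjustment". Its rows are intercept, treatment arm (reference and crossover), scale and shape, with no covariate row and no footnote. The neighbouring logistic shell, 11.3.4.1.13, leaves its rows open and points to the covariate list in 6.2.3.
- **Use of the estimate (SAP section 15, reasons for v6.0).** The acceleration factor shrinks switchers' survival "to derive a counterfactual survival dataset upon which standard survival analysis could be undertaken". Absence of unmeasured confounders at progression is one of three stated conditions.
- **Who can cross over (SAP section 2; Protocol section 3 agrees).** Arm B patients "who have documented disease progression after a minimum of eight weeks from randomization should be offered to cross over to combination arm", subject to Sponsor agreement.
- **Expected selection (SAP section 15, reasons for v5.0).** "It has been hypothesized that patients without crossover or subsequent therapies could have a worse prognosis".
- **Covariates for another method (SAP 6.2.3, Overall survival).** IPCW has a full list of time-dependent and baseline covariates. The two-stage method has none.

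**The concern.** The two-stage method treats progression as a second baseline and compares Arm B patients who then switched with those who did not. That comparison is not randomized. It estimates a drug effect only if the prognostic differences between the two groups at progression are in the model that produces the acceleration factor. With a crossover indicator alone, even the confounders that the trial measures are left out.

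The two checks do not fill the gap. A logistic regression can show which measured factors predict crossover, and a PFS comparison can show that switchers progressed later. Neither adjusts the survival model, and neither can detect confounders that were not measured. The PFS comparison also tends to differ by design, because patients who progress before week 8 cannot be in the crossover group. The SAP states no consequence if it does differ.

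At stake is one of the crossover-adjusted OS hazard ratios. If switchers would have lived longer anyway, that advantage is labelled drug effect and removed from Arm B. SAP 6.2.3 presents this method, with RPSFT and IPCW, as a way to an unbiased estimate of the survival effect.

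**Working it through.** **1. Figures in the documents.** The plan gives no figure for this adjustment, so there is none to reproduce. The death counts in the Protocol notes agree with each other: 123 + 72 = 195, and 195/255 = 76.5%. Arm B contributes 72 deaths.

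**2. How far the eight-week rule selects.** The planning examples for control median PFS are 10, 12 and 16 weeks (SAP 5.2). If PFS is exponential (assumption), the share of Arm B with a PFS event before week 8 is 1 − 2^(−8/median): 43%, 37% and 29%. None of these patients can cross over.

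**3. The bias in closed form.** In the shelled model, log T = b0 + b1·X + σε, where T is survival after progression and X = 1 for crossover. The acceleration factor (AF) is exp(b1), and a switcher's T becomes T/AF. Suppose that there is no drug effect, that half the patients are fit, and that fit patients survive r times as long after progression. Then AF is approximately r^(qc − qn), where qc and qn are the fit shares of the crossover and no-crossover groups.

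Example: median PFS 12 weeks, so 63% pass week 8. Crossover probability is 0.8 if fit and 0.5 if unfit, and r = 2.
- Crossover, fit: 0.5 × 0.63 × 0.8 = 0.252. Crossover, unfit: 0.5 × 0.63 × 0.5 = 0.157. So qc = 0.252/0.409 = 0.615.
- No crossover, fit: 0.5 − 0.252 = 0.248. No crossover, unfit: 0.5 − 0.157 = 0.343. So qn = 0.248/0.591 = 0.420.
- AF ≈ 2^0.195 = 1.145. The simulation below gives 1.13.

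**4. Simulation with no drug effect on PFS or OS.** There were 2,000 runs per scenario. Assumptions that are not in the documents: 170 and 85 patients, control median PFS 12 weeks, half of patients fit, and the crossover probabilities and r in the table. Accrual of 60 months plus 24 months of follow-up matches the Protocol. These settings give 34–44% crossover in Arm B and 200–208 deaths. The Weibull model holds the crossover indicator only, and a Cox model follows the shrinking. In the linked columns, median time to progression is multiplied by 1.41 for fit patients and divided by 1.41 for unfit patients.

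| Crossover probability, fit / unfit | r | AF, unlinked | HR, unlinked | AF, linked | HR, linked |
|---|---|---|---|---|---|
| 0.7 / 0.7 | 1 | 1.00 | 1.00 | 1.00 | 1.00 |
| 0.7 / 0.7 | 2 | 1.01 | 1.00 | 1.10 | 0.97 |
| 0.8 / 0.5 | 1.5 | 1.08 | 0.96 | 1.15 | 0.94 |
| 0.8 / 0.5 | 2 | 1.13 | 0.95 | 1.24 | 0.92 |
| 0.9 / 0.4 | 1.5 | 1.13 | 0.95 | 1.21 | 0.92 |
| 0.9 / 0.4 | 2 | 1.25 | 0.91 | 1.37 | 0.88 |
| 0.9 / 0.4 | 3 | 1.43 | 0.88 | 1.64 | 0.85 |
| 0.9 / 0.2 | 2 | 1.39 | 0.90 | 1.49 | 0.87 |
| 0.9 / 0.2 | 3 | 1.71 | 0.85 | 1.87 | 0.82 |

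The second row, linked, is the eight-week rule acting alone. An AF of 1.25 cuts switchers' post-progression survival by 1 − 1/1.25 = 20%. The unadjusted ITT HR stays at 0.995–1.007 throughout. Recensoring moves the adjusted HR by about 0.005 or less. A separate simulation with continuous frailty (variance 0.1, 0.25 and 0.5, 171/84 patients, 43% crossover, all assumed) gave 0.96, 0.89–0.94 and 0.85–0.90.

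**5. Rejection rate.** Naive one-sided 2.5% rejection in favour of plitidepsin is 7–29% with selection, against 2–4% for ITT. Not all of that is selection: without selection the two-stage test already rejects in 5–6% of runs, because the Cox standard error treats the estimated AF as known.

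**6. Effect of a repair.**
- With the prognostic factor itself in the Weibull model, AF is 0.99–1.01 and the HR 0.99–1.00.
- With time to progression plus an imperfect marker (squared correlation with log frailty 0.3–0.6, 300 runs per scenario), the HR is 0.96–0.98, against 0.88–0.95 with the indicator only.
- When the eight-week rule is the only selection, restricting the comparator to patients who progressed at week 8 or later gives 0.99–1.00 without covariates, against 0.92–0.98 unrestricted.
- Restriction alone does not deal with selection on fitness. In the example of step 3 it lowers qn to 0.2/(0.2 + 0.5) = 0.286, so AF rises to 2^0.329 = 1.26.

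**The case against.** The strongest reply is that the SAP text does not exclude covariates. It adopts a published method by reference and lists the stepwise logistic model among the analyses needed for the adjustment. A reader might infer that the SAP states a model with a crossover indicator only. It does not: the sentence is silent, and the point rests on the table shell. Still, that shell names its terms, while the one beside it refers to a covariate list. A programmer following the SAP would fit no covariates.

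A reader might also infer that the adjusted hazard ratio must favour plitidepsin. The documents do not support that. With no selection it is 1.00, and they call the number of switchers indeterminate. Patients who did not cross over may have received other antitumor therapy, which, if effective, would pull the acceleration factor the other way. The simulations did not model this.

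The consequence is also limited. This is one of five crossover analyses, run only if OS appears substantially influenced by crossover, and labelled supportive. IPCW carries its own covariate list, a forest plot sets the OS hazard ratios side by side, and the baseline and PFS tables would reveal imbalance. All of this stands and keeps the point at the level of an improvement.

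**Conclusion.** The point holds in conditional form. As written and shelled, the two-stage model takes no account of measured prognosis at progression. The eight-week rule, Sponsor agreement and the sponsor's recorded hypothesis all suggest that crossover patients have the better prognosis. If so, the adjusted OS hazard ratio is biased in favour of plitidepsin.

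Under no drug effect it is about 0.95–0.97 with mild to moderate selection or the eight-week rule alone, about 0.82–0.91 with strong selection, and 1.00 with none. Moderate selection combined with a link between time to progression and prognosis falls between, at 0.92–0.94. The direction follows from the method once selection is granted. The size rests on assumed arm sizes, crossover rate and strength of selection.

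One supportive sensitivity analysis of a secondary endpoint is affected. Nothing here touches primary PFS or ITT OS.

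**What to change.** In SAP 6.2.3 and Table 11.3.4.1.15:

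1. Put into the Weibull model a short, named set of covariates measured at progression and already listed for IPCW, for example ECOG, M-protein, LDH and hemoglobin, plus time to progression.
2. Define the comparator as Arm B patients who progressed at eight weeks or later without crossing over, since only they were eligible. Make this change together with the first, not in place of it.
3. Derive the acceleration factor from that model, and describe the logistic regression and PFS comparison as descriptive.

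The trial already collects these data: ECOG and hemoglobin on Days 1 and 15, LDH and M-protein each cycle (Protocol Schedule of Assessments and Table 4). SAP v6.0 refers to a meeting on 12 June 2017, after the OS analysis of 19 May 2017. The terms should therefore be fixed in writing before the model is run, with the date stated.

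The cost is a few lines of SAP text and a wider confidence interval, because Arm B has 72 deaths and the restriction leaves fewer. The bias is reduced, and removed only as far as the covariates capture prognosis. The report should say so.
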